Primary Endpoint:	Accuracy of diagnosis of common bile duct stones in patients with low and intermediate risk by novice combined with AI-assisted and expert
Secondary Endpoints:	1) Sensitivity, specificity, NPV, and PPV for the diagnosis of common bile duct stones in low and intermediate risk patients 2) Detection rate of gallstone lesions 3) Missed detection rate of gallstone lesions 4) Detection rate of bile duct lesions(all bile duct lesions including gallstones) 5) Missed rate of bile duct lesion(all bile duct lesions including gallstones) 6) Number of bile duct standard station scans 7) scan time 8) Incidence of Adverse Events
Trail design:	Single center, prospective, tandem, randomized control
Participants:	Male and female subjects aged 18 years and older at low to moderate risk of suspected common bile duct stones are required to undergo ultrasound endoscopy, voluntarily provide endoscopic imaging and sign an informed consent form
Sample size:	184 samples were collected to explore the sample distribution, and then calculate the sample size according to the sample distribution.

[figure not shown]
Study Process:	Determination of entry and exclusion criteria was performed before performing ultrasound endoscopy, and subjects who met all entry criteria and did not meet all exclusion criteria were included in the study. All patients who met the entry-exclusion criteria were randomized 1:1 into two groups A and B for a tandem, randomized controlled trial. Patients in group A were first swept by the novice endoscopist with the assistance of a deep learning-based bile duct sweep system during the examination, and then re-swept by the specialist without AI assistance after the sweep was completed; patients in group B were first swept by the specialist without AI assistance during the examination, and then swept by the novice endoscopist with AI assistance after the sweep was completed. Novice physicians and specialists were unaware of each other's sweeps, and subjects were unaware of their grouping. The recorder recorded the bile duct sweep results of the novice physicians and specialists during the 2 examinations in real time, and the patients were still to be followed up for 6 months after the procedure (telephone follow-up in months 1, 2, 3, and 6 with instructions to review liver function and abdominal ultrasound), and the end of the follow-up was the end of the study; the results of the collected patient examinations were transmitted to an independent data analysis group for review, and the review group was unaware of the subgroup of subjects.
Security:	Safety incidents shall be evaluated and reported according to the quality management measures for clinical trials of medical devices

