6.3.3. Intraoperative Managements

- 1) Subject position: lateral recumbent position with appropriate restraint.
- 2) Insertion route: chosen according to the subject's actual condition, usually transoral.
- 3) Bile duct sweep with novice followed by expert or expert followed by novice depending on the grouping.
- 4) Intraoperative abnormal findings must be scrutinized through standard clinical procedures, and photographs must be kept for documentation of any findings during ultrasound endoscopy.

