8.2. Methods

- 1) Means and standard deviations for continuous variables with equal distribution and medians for non-equal distribution; percentages for categorical variables.
- 2) Continuous variables were compared by t-test (e.g., age) or Mann-Whitney U test (bilirubin, aspartate aminotransferase, alkaline phosphatase, alanine aminotransferase).
- 3) Categorical variables were compared using McNemar's test.

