8.3. Sample Size Calculation

For the sample size determination, the level of bilateral significance was 5% ($\alpha=5\%$), 80% certainty ($\beta=20\%$), and based on previous reports of 90% diagnostic accuracy of endoscopists for common bile duct stones, a non-inferiority test of novice combined with AI non-inferiority to expert was performed, and a total of 147 patients were calculated to be enrolled. Assuming a 20% shedding rate, a total of 184 subjects were expected to be enrolled.

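### Sweep order is the only randomised factor, yet no analysis by order is planned: a shared order effect nearly cancels, but an unequal one could bias the comparison unseen

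*Combined protocol and SAP*

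**What the plan says.** Every patient is swept twice in one examination, once by the AI-assisted novice and once by the unassisted expert. The Summary (Study Process) says "All patients who met the entry-exclusion criteria were randomized 1:1 into two groups A and B": novice first in A, expert first in B. Section 6.3.3 repeats this: "Bile duct sweep with novice followed by expert or expert followed by novice depending on the grouping". Nothing else is randomised.

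The same part of the Summary says that novices and experts did not know each other's sweep results. Section 6.5 names only the subjects and the data review panel as blinded, and no procedure for keeping the second reader unaware is described.

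On analysis, section 8.2 says "Categorical variables were compared using" McNemar's test. Sections 8.2 to 8.4 mention no order or group term, no results by group, no carry-over check and no first-sweep analysis. Section 8.3 describes the comparison as follows: "a non-inferiority test of novice combined with AI non-inferiority to expert was performed". Section 6.3.4 has the recorder note each subject's group, so the data for an analysis by order will exist.

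**The concern.** The second sweep may not be equivalent to the first. The patient has been sedated longer, and the scope has already been through the region. Section 6.3.3 also requires abnormal findings to be examined and photographed during the procedure, so a positive first sweep could change the session that the second reader enters. The readers differ greatly in experience (section 3: fewer than 25 independent cases for novices, at least 3 years of EUS for experts), so an equal effect of going second cannot be taken for granted.

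Randomised order guards against part of this, but the plan never uses it in the analysis. Two things are at stake: a small bias if A and B end up unequal in size, and a possibly larger bias if going second affects one reader more than the other. Nothing planned would show either, and any look by order after the results are known would be post hoc.

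**Working it through.** **The plan's own figure.** Section 8.3: "a total of 147 patients were calculated to be enrolled" and "Assuming a 20% shedding rate, a total of 184 subjects were expected to be enrolled". 147 / 0.80 = 183.75, rounded up to 184, so the dropout step reproduces. The 147 itself cannot be checked, because neither the non-inferiority margin nor the paired discordance is stated. The order argument does not depend on it; 147 is used below only as the evaluable number.

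**Inputs.** From the plan: 147 evaluable patients, 1:1 order, and 90% accuracy ("based on previous reports of 90% diagnostic accuracy of endoscopists for common bile duct stones"), applied here to both readers because no separate figure is given for the novice. Assumed: the effects of going second, and a discordance of 0.18 (two independent readings at 90%: 2 × 0.9 × 0.1).

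**Model.** Let D be the true novice-minus-expert accuracy difference, and dN and dE the changes in novice and expert accuracy when each sweeps second.
- Expected paired difference in A (expert second): D − dE.
- Expected paired difference in B (novice second): D + dN.
- Bias of the pooled difference: (nB·dN − nA·dE) / (nA + nB). With nA = nB this is (dN − dE)/2.

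**Shared effect, dN = dE = 5 points.**
- 74/73: (73 − 74) × 5 / 147 = −0.03 points.
- 80/67: (67 − 80) × 5 / 147 = −0.44 points.
- 85/62: (62 − 85) × 5 / 147 = −0.78 points.

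Under simple randomisation (an assumption; the plan says only 1:1), the 95% limit for the proportional imbalance is 1.96 / √147 = 0.16. The 85/62 split is 23 / 147 = 0.156, so it lies near that limit.

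**Unequal effect, equal groups.**
- dN = 5, dE = 0: +2.5 points, in the novice's favour.
- dN = 0, dE = 5: −2.5 points, in the expert's favour.

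**What each remedy does.**
- *Equal-weight average of A and B:* [(D − dE) + (D + dN)] / 2 = D + (dN − dE)/2. The imbalance part goes; the 2.5 points from an unequal effect stay.
- *A-versus-B contrast of paired differences:* (D + dN) − (D − dE) = dN + dE. This is the sum of the two effects, whereas the bias depends on their difference. Effects of 5 and 5 give a contrast of 10 with no bias; effects of +5 and −5 give a contrast of 0 with a bias of 5. Its SE at 73.5 per group is √(2 × 0.18 / 73.5) = 7.0 points, so two-sided 5% power is about 11% for a true contrast of 5 points and 30% for 10.
- *First sweeps only (novice + AI in A versus expert in B):* this estimates D with neither dN nor dE in it. SE = √(2 × 0.9 × 0.1 / 73.5) = 4.95 points, and the 95% half-width is 1.96 × 4.95 = 9.7 points. The paired analysis of 147 has SE √(0.18 / 147) = 3.5 points.

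**The case against.** The strongest reply is that counterbalancing already does the work. A reader might infer that any order effect passes straight into the novice-versus-expert difference. It does not: a shared effect helps the expert in A and the novice in B and cancels, leaving under 1 point even at 85/62. A shared 5-point effect adds about 0.05² = 0.0025 to a per-pair variance of about 0.18, roughly 1.4%. This part of the reply stands.

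A reader might also infer that the bias favours non-inferiority. The documents do not support a direction. Longer sedation could worsen a second sweep, and the expert could gain as much as the novice or more. A 10-point novice gain would be the ceiling: from 90% it means a correct diagnosis on every second sweep.

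Nor can the bias be expressed as a fixed share of the margin, because no margin is stated. At one-sided 0.025, 80% power and equal accuracy, 147 pairs imply a margin of √(7.849 × discordance / 147): 5.2 points at a discordance of 0.05, 9.8 at 0.18 and 10.3 at 0.20.

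Finally, the Summary says that the readers were unaware of each other's sweeps, which would close the main information route. It is a real protection on paper, though section 6.5 does not list the readers as blinded and no masking method is given. It also does not touch physical effects such as time under sedation. Section 8.2 does not say in so many words that all pairs are pooled; that is the natural reading of one unqualified McNemar test.

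What survives is the omission: nothing by order is prespecified.

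**Conclusion.** The point holds as a gap in the analysis plan, not as a demonstrated bias. The randomised factor is not used in any planned analysis. For an assumed shared 5-point effect, the consequence is negligible with near-equal groups and 0.4 to 0.8 points at 80/67 to 85/62. Some inequality is plausible: no blocking is described, section 8.3 allows for 20% dropout, section 6.4.3 rules out replacement of discontinued subjects, and section 8.4 makes the per-protocol set the main one.

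For an unequal effect, the bias is half the inequality, in either direction: 2.5 points for an assumed 5-point effect in one reader only. The documents give no information on the size of either effect. An order-stratified estimate cannot remove this second bias. Only the first-sweep comparison is free of carry-over, and it is too imprecise to serve as the primary analysis. The change is worth making because it costs almost nothing and must be fixed before the results are seen.

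**What to change.** In section 8.2:

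1. Define the primary estimate as the order-stratified paired accuracy difference, the equal-weight average of the differences in groups A and B, with its 95% CI. State that this removes the effect of unequal group sizes only.
2. Report the paired difference separately in A and in B as a descriptive order check. Note that the A-versus-B contrast estimates the sum of the two readers' second-sweep effects and has low power, so a null result is not evidence that there is no carry-over.
3. Prespecify a first-sweep-only comparison (novice + AI in A versus expert in B) as the carry-over-free sensitivity analysis, with its expected 95% half-width of about 9.7 points at 147 patients and 90% accuracy.

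The cost is a few lines of text and analysis. Group is already recorded, and no extra patients or procedures are needed. The downside is a sensitivity result that will be imprecise and should be presented as such.

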1.1 Time and Event Tables

Events	Screening period (d -30~0)	The day of Ultrasound Endoscopy (d 0)	Follow up ((d 0~180)
Informed Consent	X		
Basic characteristics	X		
Medical history/surgical history	X		
Physical Examination	X		
Inclusion/Exclusion Criteria		X	
Ultrasound Endoscopy		X	
Concomitant treatment	X	X	
Concomitant medication	X	X	
Adverse Events		X	X
Follow-up results (6 months)			X
Research completed			X

1.2 Flow chat

2. Introduction

The incidence of gallstones has been increasing in recent years, up to 10-15% in developed countries, and is still increasing at a rate of 0.6% per year. It is estimated that common bile duct stones (CBDS) are present in about 10-20% of patients with symptomatic bile duct stones. Each year, common bile duct stones lead to acute complications such as biliary obstruction, cholangitis and acute pancreatitis in a large number of patients, seriously endangering their lives and health. In addition, Diagnostic Related Group (DRG) analysis shows that each episode of common bile duct stone costs \$9,000, and acute pancreatitis that progresses from common bile duct stones can result in 275,000 hospitalizations and \$2.6 billion in costs each year, imposing a significant

7 / 25

economic and health burden on society. Therefore, timely diagnosis of common bile duct stones and intervention for them are crucial. Endoscopic retrograde cholangiopancreatography (ERCP) is the method of choice for the diagnosis and treatment of CBDS, and guidelines recommend stone extraction for all patients with CBDS who are physically fit enough to tolerate ERCP operations. However, ERCP is a highly demanding and risky operation with the potential for serious complications such as PEP (incidence 2.6-3.5%). How to diagnose choledocholithiasis early and accurately, achieve timely patient intervention to improve prognosis, and avoid unnecessary medical operations to reduce risks are our current challenges to be solved.

The European Society for Gastrointestinal Endoscopy (ESGE) and the American Society for Gastrointestinal Endoscopy (ASGE) recently updated their guidelines for the endoscopic management of patients with suspected common bile duct stones, providing risk stratification for more accurate management in the evaluation and treatment of suspected CBDS. Based on ESGE risk stratification criteria, patients with features of cholangitis or common bile duct stones on abdominal ultrasound are classified as high risk, patients with abnormal liver function tests (LFTs) and/or abdominal ultrasound showing CBD dilatation are classified as intermediate risk, and patients with normal liver function tests and abdominal ultrasound are classified as low risk. It is recommended that patients in the intermediate risk group for CBDS and in the low risk group for whom the physician still has a high suspicion of CBDS be recommended to undergo ultrasound endoscopy (EUS) or magnetic resonance cholangiopancreatography (MRCP) to determine the presence of CBDS, depending on the local level of care. In addition, a cost-effectiveness analysis showed that MRCP would be the preferred test when the predicted probability of CBDS is less than 40%, while EUS is the preferred test when the predicted probability is 40%-90%. Compared to MRCP, EUS is widely available but has a steep learning curve. the ASGE guidelines state that a minimum of 225 EUS operations are required to qualify, while ESGE states that a minimum of 300 operations are required. However, this experience can only be gained at training centers that perform a large number of cases. Thus, the training of novice physicians in resource-limited areas is a huge challenge, which leaves a significant shortage of experienced ultrasound endoscopists and poor performance in the actual diagnosis of common bile duct stones, greatly limiting the popularity of ultrasound endoscopy.

AI technology has developed rapidly in the medical field in recent years, and several studies have shown that the diagnostic capability of AI has surpassed that of human experts in certain diseases, and there are also related studies that confirm the feasibility of AI application in ultrasound endoscopic image recognition. In our previous research, using AI technology to assist ultrasound endoscopists in film reading can significantly improve the accuracy of ultrasound image localization and anatomical marker segmentation by physicians, and we successfully built a deep learning-based bile duct segmentation and site identification system. Based on this, we develop a deep learning-based bile duct sweep system to assist novice ultrasound endoscopists in performing bile duct sweeps to identify common bile duct stones. The AI-based technology allows novice ultrasound endoscopists to obtain diagnostic quality equivalent to that of experts with minimal training, which helps to detect choledochal stones in a timely manner and improve their diagnostic accuracy for choledochal stones, alleviating the current shortage of experienced endoscopists and enabling early diagnosis and precise treatment of patients.

3. Patient Selection

The subject population of ultrasound endoscopy patients in this study was male and female subjects aged 18 years (and older) at low to intermediate risk of suspected common bile duct stones who were required to undergo ultrasound endoscopy, voluntarily provided endoscopic imaging and signed an informed consent form, and such patients were enrolled in the study.

Patients not meeting the inclusion criteria or meeting exclusion criteria will not be considered for participation in the study. Patients who met all criteria and signed informed consent may be excluded from the study due to:

- Endoscopists' professional advices/medical reasons (only under very limited conditions to avoid researcher bias).
- Withdraw informed consent.

Novice ultrasound endoscopists in this study were defined as endoscopists with 3 or more years of gastrointestinal experience and less than 25 cases of independent ultrasound endoscopy; experts were defined as endoscopists with at least 3 years of ultrasound endoscopy experience.

3.1. Inclusion criteria

All patients meeting the following criteria will be considered for participation in the study:

- 1) Males and females aged 18 years and older who are suspected of having common bile duct stones at intermediate to low risk, where intermediate-risk patients are those with normal liver function but with abdominal ultrasound suggestive of bile duct dilatation, and low-risk patients are those with normal abdominal ultrasound and liver function but whose physicians still suspect common bile duct stones;
- 2) Able to read, understand and sign an informed consent;
- 3) The investigator believes that the subjects can understand the process of the clinical study, are willing and able to complete all study procedures and follow-up visits, and cooperate with the study procedures.

3.2. Exclusion criteria

All patients meeting the following criteria will not be considered for participation in the study:

- 1) Patients at high risk of common bile duct stones. High-risk patients are those with common bile duct stones detected by abdominal ultrasound, patients with manifestations of cholangitis or hospitalized patients with a history of gallbladder stones with pain, bile duct dilatation and jaundice;
- 2) Have drug or alcohol abuse or mental disorder in the last 5 years;
- 3) Pregnant or lactating women;
- 4) Altered anatomy due to previous history of upper gastrointestinal surgery;
- 5) Patients with advanced tumors resulting in abnormal upper gastrointestinal anatomy;

- 6) High-risk diseases or other special conditions that the investigator considers the subject unsuitable for participation in the clinical trial.

3.3. Definition of enrollment

After participants signed informed consent, they were regarded as enrolled. The sign time was the enrollment time, and was recorded in CRF.

4. Endpoints

4.1. Primary Endpoint

Accuracy of novice combined with AI-assisted and expert in the diagnosis of common bile duct stones in low to intermediate risk patients: ERCP and 6-month follow-up results as gold standard. A true positive was defined as CBD stones detected by EUS and the presence of CBD stones confirmed at ERCP; a false positive was defined as CBD stones detected by EUS and the absence of CBD stones confirmed by ERCP; a true negative was defined as CBD stones not detected by EUS and as CBD stones detected at 6-month follow-up; a false negative was defined as CBD stones not detected by EUS and subsequent ERCP or CBD stones were detected at 6-month follow-up.

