6.3.4. Post-operative Managements

- 1) Routine postoperative care.
- 2) Subjects were observed until awakening.

- 3) Those without choledochal stones detected were followed up for 6 months (1st, 2nd, 3rd, and 6th months by telephone and instructed to review liver function and abdominal ultrasound).
- 4) Examination information, such as subject grouping, examining physician, examination time, sedation status, number of common bile duct stones found, and number of bile duct site scans, was recorded by the recorder.
- 5) Images, videos, and case data of the examination were collected.

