6.5. Blindness and Uncovering Blindness

The study was blinded to the subjects, who were unaware of their grouping, and to the data review panel, whose members were unaware of the subjects' grouping.

Unblinding or blinding-breaking, i.e., presenting randomization results to subjects or evaluators, should be protected by the investigator whenever possible. Unblinding of randomization results for a single subject may lead to the disclosure of randomization results for other subjects, and any disclosure of randomization results can have a significant impact on the statistical analysis. Approach blinding disclosures with caution in general, and consider unblinding in the following circumstances:

- 1) Endangering the safety of the subject: For example, in some serious adverse events, the subject needs to know the randomization results to inform other physicians to take appropriate emergency treatment.
- 2) Endangering assessor safety: When the assessor faces a safety hazard and needs to know the randomization results.
- 3) Study compliance: For partial compliance reasons, disclosure of randomization results to the appropriate authorities or the public is required in specific circumstances, such as for unanticipated adverse events that require disclosure of the study system and the cases in which it is involved.
- 4) Other regulatory reasons.

7. Basis of study protocol and risk/benefit analysis

The use of a deep learning-based bile duct scanning system provides information to novice endoscopic ultrasound practitioners on the diagnosis and treatment of common bile duct stones, which does not provide a final diagnosis, the novice doctors make their own diagnosis and follow-up diagnosis and treatment on the basis of the tips from the bile duct site identification and common bile duct stones, in the end, the results of endoscopic sonography were compared with those of novices and experts, and the results of experts were taken into account when they were inconsistent.

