7.5. Risk minimization

In this study, when the software malfunctioned, novice doctors and experts could still operate under their own judgment without affecting the routine treatment measures, and when the judgment of the two did not agree, the expert results prevailed, which greatly reduced the risk of the trial.

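### The four outcome cells in 4.1 do not carry through its composite reference, so some readings fit no cell; if those pairs are dropped, the paired non-inferiority comparison can be biased

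*Combined protocol and SAP*

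**What the plan says.** Section 4.1 (Primary Endpoint) sets the reference as "ERCP and 6-month follow-up results as gold standard" and then defines four cells:

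- True positive: "A true positive was defined as CBD stones detected by EUS and the presence of CBD stones confirmed at ERCP".
- False positive: "a false positive was defined as CBD stones detected by EUS and the absence of CBD stones confirmed by ERCP".
- True negative: "a true negative was defined as CBD stones not detected by EUS and as CBD stones detected at 6-month follow-up". A negation is evidently missing; I read it as no stone found at follow-up.
- False negative: a negative EUS with a stone found at ERCP or at 6-month follow-up. This is the only cell that uses both parts of the reference.

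Each patient is swept by both readers. Section 8.2 compares categorical variables with McNemar's test, and section 8.3 describes a non-inferiority test of novice+AI against the expert.

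On disagreement, section 7.5 says that "when the judgment of the two did not agree, the expert results prevailed". The opening text of section 7 says only that "the results of experts were taken into account when they were inconsistent", and the same sentence has novices make their own diagnosis and go on to further diagnosis and treatment. Section 6.3.3 adds: "Intraoperative abnormal findings must be scrutinized through standard clinical procedures".

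On follow-up, the Study Process entry in section 1 follows patients in general. Section 6.3.4 is narrower: "Those without choledochal stones detected were followed up for 6 months". It does not say by which reader.

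**The concern.** In a paired comparison, the patients on whom the readers disagree determine the difference. A primary endpoint therefore needs a rule that scores both readings in every such patient who has a reference result. The cells in 4.1 do not give one. If ERCP and follow-up depend on the expert's result, the comparator's call decides whether the test reading counts, while the expert's own reading remains scorable. Losing pairs in that way is not random. It can hide a real deficit of novice+AI or a real advantage. Sections 4.1, 8.2 and 8.4 do not say what happens to a reading that fits no cell.

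**Working it through.** **Plan's own figure.** 147/(1 - 0.20) = 183.75, rounded up to 184, so the dropout inflation in 8.3 reproduces. The 147 itself cannot be checked because no margin or discordance is stated. It serves here only as the number of pairs.

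**Step 1: gaps in the cells, whoever gets ERCP.** A positive EUS without ERCP is neither a true nor a false positive. A negative EUS with a clear ERCP and no follow-up is neither a true nor a false negative. This follows from the text alone.

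**Step 2: add one inference.** Suppose ERCP follows the expert's call and follow-up reveals true status. Concordant patients are then scored for both readers. The discordant ones are scored as follows:

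| Discordant patient | Expert | Novice+AI |
|---|---|---|
| A: stone, only novice positive | FN | TP only if ERCP follows; otherwise no cell |
| B: no stone, only novice positive | TN | no cell |
| C: no stone, only expert positive | FP | TN only if also followed |
| E: stone, only expert positive | TP | FN |

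Under the follow-up in 6.3.4, B and C are lost, and A too if a stone seen at follow-up is not confirmed at ERCP. Under the follow-up in section 1, C is kept and B is lost.

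**Step 3: illustration.** All reader rates are assumed; the documents give only 90% endoscopist accuracy (8.3). Prevalence p = 15% is the midpoint of the 10-20% in section 2, which describes patients with symptomatic bile duct stones, not this trial's population. Expert sensitivity/specificity is 90/90, novice+AI 85/80, errors independent, and unscored pairs are dropped.

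- A = p(se_n - se_n·se_e) = 0.15(0.85 - 0.765) = 0.01275
- E = p(se_e - se_n·se_e) = 0.15(0.90 - 0.765) = 0.02025
- B = (1 - p)(sp_e - sp_n·sp_e) = 0.85(0.90 - 0.72) = 0.153
- C = (1 - p)(sp_n - sp_n·sp_e) = 0.85(0.80 - 0.72) = 0.068

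True difference = A + C - B - E = -0.0925.

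- B and C dropped: (A - E)/(1 - B - C) = -0.0075/0.779 = -0.0096. Pairs lost: 147 × 0.221 = 32.5.
- A, B and C dropped: -E/(1 - A - B - C) = -0.02025/0.76625 = -0.0264. Pairs lost: 147 × 0.23375 = 34.4.
- Only B dropped: (A + C - E)/(1 - B) = 0.0605/0.847 = +0.0714. Pairs lost: 147 × 0.153 = 22.5.

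**Step 4: how far this depends on the assumptions.**

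- *Error correlation 0.5.* Subtract 0.5·√(sp_n(1 - sp_n)sp_e(1 - sp_e)) inside the brackets of B and C, and the same with sensitivities for A and E. Then A = 0.00472, B = 0.102, C = 0.017, E = 0.01222, and the true difference is unchanged. The three results become -0.9, -1.4 and +1.1 points. Pairs lost in the first two cases fall to 17.5 and 18.2.
- *Prevalence 10% to 20%, independent errors.* True -9.5 to -9.0 becomes -0.7 to -1.3 with B and C dropped, and -1.8 to -3.5 with A dropped too.
- *Novice+AI 85/95.* B = 0.03825 and C = 0.08075. True +3.5 becomes -0.0075/0.881 = -0.9 points with B and C dropped, so the bias runs against the novice.
- *Equal specificity: prevalence 40%, expert 85/97, novice+AI 95/97.* A = 0.057, E = 0.017, B = C = 0.01746. True +4.0 becomes 0.04/0.96508 = +4.1 points with B and C dropped.

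The last two cases show that no simple rule on the readers' specificity fixes the direction. Because 8.3 states no margin, I do not turn these differences into chances of passing.

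**The case against.** The strongest reply is that the named gold standard is the composite. An ordinary reading of it scores every discordant patient who has either ERCP or completed follow-up, and the false-negative cell shows that the composite was meant. Results also go to an independent review group. On that reading no bias arises. This reading is available, and no passage says that readings without a cell are excluded. But it is not what three of the four definitions say, and blinding the review group to allocation supplies no scoring rule.

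A reader might infer that 4.1 itself makes the novice's score depend on the expert's call. It does not. Its cells depend on whether ERCP was done, and 6.3.4 names no reader. The dependence is inferred mainly from 7.5, a sentence about risk that opens with software malfunction. Section 7 is weaker on the point, and 6.3.3 and section 7 leave room for a novice-only finding to be pursued. If every patient positive on either reading had ERCP, the gap for novice positives would close. That part of the objection stands, so the bias must be stated as conditional.

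A reader might also infer that the bias favours non-inferiority. The counter-example in the working rules that out as a general statement, and the documents give no sensitivity or specificity for either reader.

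**Conclusion.** Section 4.1 is deficient as written: two kinds of reading have no cell, and the true-negative definition lacks its negation. That conclusion rests on the text alone. The bias is conditional on three things: that ERCP follows the expert's result on disagreement, that the narrow cells rather than the composite are applied, and that unscored pairs are dropped.

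Under the assumed rates, a true -9.25 points moves to between -2.6 and +7.1, with about 32-34 of 147 pairs lost in the two cases without C, or about 18 at error correlation 0.5. These figures show what can happen; they do not predict this trial. Size and direction depend on reader error rates, prevalence, scope of follow-up and handling of unscored readings, none of which the documents settle. The point should be fixed before readings are scored, so that the primary endpoint does not depend on a choice made after discordant results are seen.

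**What to change.** Replace the four definitions in 4.1 with one patient-level reference, applied to each reader separately:

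- Stone present: found at ERCP or at any time to month 6.
- Stone absent: otherwise, with a clear ERCP, or with no ERCP and no stone through month 6.
- A positive call is a true positive if a stone is present and a false positive if absent. A negative call is a false negative or a true negative likewise. This also corrects the true-negative wording.
- No reading is left unscored because of the other reader's call. A patient with neither ERCP nor month-6 follow-up has a missing reference for both readers.

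State in 8.2 that the paired comparison uses this reference. Reconcile section 1 (Study Process), 4.1, 6.3.4, the opening of section 7, and 7.5 on who is followed and how discordant patients are verified. This does not prescribe who gets ERCP.

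A sensitivity analysis that counts novice-only positives without ERCP as all wrong and then as all right is optional, because its bounds are wide. In the illustration, with all such positives lacking ERCP, A + B = 0.16575 (about 24 of 147). The bounds are C - E - (A + B) = -11.8 points and C - E + (A + B) = +21.4 points, around a true -9.25.

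The cost is mainly wording, since both readers' results are already recorded in real time. There are two downsides. Stones that pass, or that telephone-directed follow-up misses, count against a novice who saw them. And if the follow-up in 6.3.4 governs, some patients may have a missing reference, so unchanged procedures may not cover everyone.
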